9.2.2 Method of Detecting AEs and SAEs

AEs can be spontaneously reported or elicited during open-ended questioning, examination, or evaluation of a participant. Care should be taken not to introduce bias when collecting AEs and/or

SAEs. Inquiry about specific AEs should be guided by clinical judgment in the context of known AEs, when appropriate for the program or protocol.

9.2.3 Follow-up of AEs and SAEs

- Non-serious AEs should be followed to resolution or stabilization, or reported as SAEs if they become serious (see Appendix 3).
- Follow-up is also required for non-serious AEs that cause interruption or discontinuation of study intervention and for those present at the end of study intervention as appropriate.
- All identified non-serious AEs must be recorded and described on the non-serious AE page of the CRF (paper or electronic). Completion of supplemental CRFs may be requested for AEs and/or laboratory test result abnormalities that are reported/identified during the study.

All SAEs will be followed until resolution, until the condition stabilizes, until the event is otherwise explained, or until the participant is lost to follow-up (as defined in Section 8.3: Lost to Follow-up).

Further information on follow-up procedures is given in Appendix 3.

9.2.4 Regulatory Reporting Requirements for SAEs

- Prompt notification by the investigator to the Sponsor of SAEs is essential so that legal obligations and ethical responsibilities toward the safety of participants and the safety of a product under clinical investigation are met.
- An investigator who receives an investigator safety report describing SAEs or other specific safety information (eg, summary or listing of SAEs) from the Sponsor will file it along with the Investigator's Brochure and will notify the IRB/IEC, if appropriate, according to local requirements.

The Sponsor or designee must report AEs to regulatory authorities and ethics committees according to local applicable laws and regulations. A suspected, unexpected serious adverse reaction (SUSAR) is a subset of SAEs and must be reported to the appropriate regulatory authorities and investigators following local and global guidelines and requirements.

9.2.5 Pregnancy

This section is not applicable for women not of childbearing potential.

If, following initiation of the study intervention, it is discovered that a participant is pregnant or may have been pregnant at the time of study intervention exposure, including at least 5 days after study intervention administration, the investigator must immediately notify the Sponsor Medical Monitor/designee of this event and complete and forward a Pregnancy Surveillance Form to the Sponsor designee within 24 hours of awareness of the event and in accordance with SAE reporting procedures described in Appendix 3.

In all cases, the study intervention will be discontinued in an appropriate manner (eg, dose tapering if necessary for participant safety).

Follow-up information regarding the course of the pregnancy, including perinatal and neonatal outcome and, where applicable, offspring information, must be reported on the Pregnancy Surveillance Form. Protocol-required procedures for study discontinuation and follow-up must be performed.

Any pregnancy that occurs in a female partner of a male participant at the time of study intervention exposure, including at least 5 days after study intervention administration, should be reported to the Sponsor or designee. For the Sponsor or designee to collect any pregnancy surveillance information from the female partner, the female partner must sign an ICF for disclosure of this information. Information on this pregnancy will be collected and recorded on the Pregnancy Surveillance Form.

If any sexual activity involving penile intercourse (eg, vaginal, anal, oral) has occurred between a male participant and a pregnant partner(s) without the use of a condom during and for at least 5 days after study intervention administration, the information should be reported to the Sponsor or designee, even if the male participant has undergone a successful vasectomy.

9.2.6 Laboratory Test Result Abnormalities

The following laboratory test result abnormalities should be captured on the Adverse Events – Non-serious and Serious Events CRF page. Paper forms are only intended as a back-up option when the electronic system is not functioning.

- Any laboratory test result that is clinically significant or meets the definition of an SAE
- Any laboratory test result abnormality that requires the participant to have study intervention discontinued or interrupted
- Any laboratory test result abnormality that requires the participant to receive specific corrective therapy

It is expected that, wherever possible, the clinical rather than the laboratory term will be used by the reporting investigator (eg, anemia vs low hemoglobin value).

9.2.7 Potential Drug-induced Liver Injury

Wherever possible, timely confirmation of initial liver-related laboratory test result abnormalities should occur prior to the reporting of a potential drug-induced liver injury (DILI) event. All occurrences of potential DILIs meeting the defined criteria must be reported as SAEs (see Section 9.2: Adverse Events and Appendix 3: ADVERSE EVENTS AND SERIOUS ADVERSE EVENTS: DEFINITIONS AND PROCEDURES FOR RECORDING, EVALUATING, FOLLOW-UP, AND REPORTING for reporting details).

A potential DILI is defined as follows:

Aminotransferase (alanine aminotransferase [ALT] or aspartate aminotransferase [AST])
elevation > 3× upper limit of normal (ULN)
AND

• Total bilirubin $> 2 \times$ ULN, without initial findings of cholestasis (elevated serum alkaline phosphatase)

AND

• No other immediately apparent possible causes of aminotransferase elevation and hyperbilirubinemia, including, but not limited to, viral hepatitis, pre-existing chronic or acute liver disease, or the administration of other drug(s) known to be hepatotoxic

9.2.8 Other Safety Considerations

Any significant worsening of conditions noted during interim or final physical examinations, ECG, radiographic imaging, or any other potential safety assessment required or not required by the protocol should also be recorded as a non-serious AE or SAE, as appropriate, and reported accordingly.

9.3 Overdose

. Overdoses that meet the regulatory definition of an SAE will be reported as SAEs (see Appendix 3).

9.4 Safety

Planned time points for all safety assessments are listed in Section 2: Schedule of Activities.

9.4.1 Physical Examinations

A complete PE will be obtained at specified time points as outlined in Section 2: Schedule of Activities. The complete PE will consist of evaluation of the following systems: general, head, eyes, ears, nose, throat, neck, cardiovascular, lungs, abdominal, extremities, neurologic, psychiatric, skin, and musculoskeletal. Complete PEs may be performed by a Doctor of Medicine, Doctor of Osteopathy, Physician's Assistant, or a Nurse Practitioner.

9.4.2 Tuberculosis Screening and Chest X-Ray

A chest x-ray and PE are considered part of the process to assess a participant's eligibility as outlined in Section 6. Chest x-ray at the screening visit is required if not already performed within 6 months of obtaining written informed consent or if documentation is not on file.

[figure not shown]
In addition to a complete PE and medical history to evaluate exposure to TB, all participants will have a screening test, an IGRA (eg, T-spot®, QuantiFERON®), preferably performed centrally. If unable to obtain central lab results (eg, repeated test due to indeterminate result), an IGRA test could be obtained locally, after consultation with the Sponsor Medical Monitor.

Participants with a positive screening test will not be eligible for the study unless they have completed at least 1 month of treatment for latent TB prior to dosing of study intervention, and the participant has a negative chest x-ray done at screening that reveals no evidence of active TB and a negative IGRA test (Quantiferon or T-spot) is confirmed prior to Day.

Protocol Amendment No.: 01

9.4.3 Electrocardiograms

12-lead ECGs should be collected at times specified in Table 2-1 and Table 2-2. All scheduled ECGs should be performed after the participant has rested quietly for at least 5 minutes in a supine position. When the timing of the measurements coincides with a blood collection, the ECG should be obtained prior to the nominal time of the blood collection, blood pressure, and pulse rate.

Protocol Amendment No.: 01

Vital Signs 9.4.7

Refer to Section 2: Schedule of Activities.

9.4.8 Clinical Safety Laboratory Assessments

Investigators must document their review of each laboratory safety report.

Participants should fast for at least 8 hours prior to sample collection at screening, on Day , and ET only. A central/local laboratory will perform the analyses and will provide reference ranges for these tests.

Table 9.4.8-1: Clinical Laboratory Assessments

Hematology				
Hemoglobin				
Hematocrit				
Total leukocyte count, including differential				
Platelet count				
Chemistry				
Aspartate aminotransferase	Total protein			
Alanine aminotransferase	Albumin			
Total bilirubin	Sodium			
Direct bilirubin	Potassium			
Alkaline phosphatase	Chloride			
Lactate dehydrogenase	Calcium			
Creatinine	Phosphorus			
Blood urea nitrogen or serum urea	Magnesium			
Uric acid	Creatine kinase			
Fasting glucose (Day , and ET only)	Creatinine clearance – screening only			
Fasting C-peptide (Day , and ET only)				
Fasting Lipid Panel				
Total C (mg/dL, mmol/L) Reflex testing will occur for direct LDL-C if TG > 40	00 mg/dL (4.52 mmol/L)			
HDL-C (mg/dL, mmol/L)				
TG (mg/dL, mmol/L)				
Note: A participant should be fasting at least 8 hours	(Day , and ET only).			
Urinalysis				
Protein				
Glucose				
Blood				
Leukocyte esterase				
Specific gravity	Specific gravity			

Protocol Amendment No.: 01

Table 9.4.8-1: Clinical Laboratory Assessments

рН

Microscopic examination of the sediment if blood, protein, or leukocytes esterase are positive on the dipstick

Serology

Serum for hepatitis C antibody, HBsAg, anti-hepatitis B core antibody, anti-HBsAb, HIV-1 and -2 antibody (HIV viral RNA or p24 antigen, if needed). At screening only.

Other Analyses

Test for drugs of abuse (urine or serum) (screening and predose on Day

Pregnancy test (women only: serum at screening, urine at Days

Follicle stimulating hormone (screening only for women only)

hsCRP - abnormalities in hsCRP levels present at baseline do not necessarily warrant participant exclusion. Please discuss with the Sponsor Medical Monitor.

Tuberculosis test (at screening only)

Abbreviations: ET, early termination; HBsAb, hepatitis B surface antibody; HBsAg, hepatitis B surface antigen; HDL-C, high-density lipoprotein cholesterol; HIV, human immunodeficiency virus; hsCRP, high sensitivity C-reactive protein; ; LDL-C, low-density lipoprotein cholesterol; RNA, ribonucleic acid; ; TG, triglycerides.

[figure not shown]
Protocol Amendment No.: 01

9.6 Immunogenicity Assessments

Not applicable.

Protocol Amendment No.: 01

Date: 29-Mar-2023 66

9.8 Optional Future Research

This protocol will include residual sample storage for optional future research, from consented participants only.

Samples kept for future research will be stored at the Sponsor-designated storage facility.

The manager of these samples will ensure that they are properly used throughout their usable life and will destroy the samples at the end of the scheduled storage period, no longer than 20 years after the end of the study or the maximum period allowed by applicable law.

Samples will be stored in a coded fashion, and no researcher will have access to the key. The key will be securely held by the investigator at the clinical site, so there is no direct ability for a researcher to connect a sample to a specific individual.

Further details of sample collection and processing will be provided to the site in the Laboratory Manual.

9.9 Other Assessments

Not applicable.

9.10 Health Economics OR Medical Resource Utilization and Health Economics

Health economics/medical resource utilization and health economics parameters will not be evaluated in this study.

10 STATISTICAL CONSIDERATIONS

10.1 Statistical Hypotheses

The primary efficacy hypothesis of this study stipulates that the proportion of participants with moderate-to-severe PsO achieving a 75% reduction in PASI score from baseline after 12 weeks of treatment with BMS-986322 will be higher than after 12 weeks of treatment with placebo.

10.2 Sample Size Determination

[figure not shown]
The sample size calculation is driven by several considerations.

The first consideration is to compare the response rate in PASI-75, the proportion of participants with moderate-to-severe PsO experiencing a 75% improvement (reduction from baseline) in PASI score from baseline after 12 weeks, between BMS-986322 and placebo arms. With a 2-sided, 2-sample Fisher's exact test at a significant level of 5%, a sample size of participants per arm will provide at least 99% power to detect a 60% increase in the PASI-75 response rate in an active arm (ie, 70% response rate) compared to placebo assuming the response rate is 10% in the placebo arm after 12 weeks of treatment. The second consideration is to assess the response rate in PASI-75 in active dose arms. With a probability of at least 99%, data from treated participants per active arm will produce a 2-sided 95% exact confidence interval (CI) with a margin of error (half-width) of at most 18.8%. In addition, administration of BMS-986322 to participants in each active treatment group provides approximately 26%, 79%, and 96% probability of observing at least one occurrence of any treatment-emergent AE that would occur with 1%, 5%, or 10% incidence rate, respectively.

Protocol Amendment No.: 01

930193109 2.0

Approved v2.0

Therefore, approximately 120 participants will be randomized in a 1:1:1:1 ratio to receive BMS-986322 (16 mg PO QD, 32 mg PO QD, or 64 mg PO QD) or placebo. Randomization will be stratified by use of previous treatment with a biologic (yes/no). Assuming a screen failure rate of about 20%, it is estimated that approximately 150 screened participants will be required to achieve the planned 120 treated participants.

10.3 Analysis Sets

For the purposes of analysis, the following populations are defined:

Population	Description
All Enrolled Participants	All participants who have agreed to participate in a clinical study following completion of the informed consent process, unless otherwise specified by the protocol.
All Randomized Participants	All participants who were randomized using IRT.
Full Analysis Set	All participants who were randomized and have received at least one dose of study intervention. This population will be used for efficacy analyses and will be analyzed as per randomized treatment.
Per Protocol Population	All participants who were randomized and have no relevant protocol deviation. The primary efficacy analysis will be repeated using this population if there are more than 10% of participants with relevant protocol deviations. Participants will be analyzed as per randomized treatment.
Safety Population	All participants who were randomized and have received at least one dose of study intervention. This population will be used for safety analyses and will be analyzed as per actual treatment received.

Abbreviation: IRT, Interactive Response Technology.

10.4 Statistical Analyses

The SAP will be developed and finalized prior to final database lock and subsequent unblinding, and it will include a more technical and detailed description of the statistical analyses described in this section. This section is a summary of the planned statistical analyses of the most important endpoints, including primary and key secondary endpoints.

A description of the participant population will be included in the CSR, including subgroups of age, gender, gender identity, race, and other study-specific populations and demographic characteristics. A description of participant disposition will also be included in the CSR.

Participant characteristics and/or demographic data may be pooled across studies for future analysis.

10.4.1 General Considerations

Categorical variables will be summarized using counts and percentages of participants falling into each category by treatment group and visit, as applicable. Continuous variables will be summarized using number of participants, mean, standard deviation, median, lower quartile, upper quartile, minimum, and maximum by treatment group and visit, as applicable and unless otherwise specified. Descriptive summaries of PK data will additionally include geometric mean and

Protocol Amendment No.: 01

Date: 29-Mar-2023 70

arithmetic percentage coefficient of variation (%CV). Tmax and similar parameters will be described by median, minimum, and maximum statistics. Change from baseline will be derived as difference of the observed value to its corresponding baseline value, where baseline is defined as the last non-missing observation prior to first administration of any study intervention and will be presented by descriptive summary statistics. Details on statistical considerations will be included in the SAP.

10.4.2 Planned Analyses

The final analysis will be conducted after conclusion of the study (ie, when the last participant has completed the study as defined in Section 5.3) and final database lock has occurred.

10.4.3 Primary Endpoint(s)

The primary objective of this study is to evaluate the response rate in PASI-75 after 12 weeks of treatment with BMS-986322. The response rate in PASI-75 is defined as the proportion of participants with moderate-to-severe PsO experiencing a 75% improvement (reduction from baseline) in PASI score at Week 12 (Day 85) and will be evaluated on the Full Analysis Set.

The safety and tolerability of BMS-986322 will be assessed by the type, frequency, relationship, severity, and seriousness of treatment-emergent AEs, clinical laboratory tests, 12-lead ECG, vital signs, and PE. Treatment-emergent AEs and study intervention-related AEs and SAEs will be summarized using counts and percentages of participants experiencing the event as well as the number of events by system organ class, preferred term, and treatment group. PE findings, vital signs, clinical laboratory test results, and ECG test results will be summarized using descriptive summary statistics for continuous variables and frequency distributions (counts and percentages) for categorical variables. All safety analyses will be performed on the Safety Analysis Set. An overview of primary efficacy and safety endpoints is given in Table 10.4.3-1.

Table 10.4.3-1: Primary Efficacy and Safety Endpoints

Primary Endpoint	Description	Time Frame
Achievement of PASI-75	At least 75% improvement in PASI score as compared to baseline, ie, percent change from baseline less than or equal to -75%	Week 12
Incidence of TEAEs	Type and frequency of TEAEs, SAEs, and TEAEs leading to treatment discontinuation Severity and causal relationship of TEAEs	30 days after last dose of study intervention or date of last follow-up, whichever is later
Clinical laboratory tests	Change from baseline and incidence of marked abnormalities	30 days after last dose of study intervention or date of last follow-up, whichever is later

Table 10.4.3-1: Primary Efficacy and Safety Endpoints

Primary Endpoint	Description	Time Frame	
12-lead ECG	Change from baseline and incidence of abnormal findings	30 days after last dose of study intervention or date of last follow-up, whichever is later	
Vital signs	Change from baseline and incidence of marked abnormalities	30 days after last dose of study intervention or date of last follow-up, whichever is later	
Physical examination	Change from baseline (weight), and incidence of abnormal findings	30 days after last dose of study intervention or date of last follow-up, whichever is later	

Abbreviations: ECG, electrocardiogram; PASI, Psoriasis Area and Severity Index; SAE, serious adverse event; TEAE, treatment-emergent adverse event.

To compare the response rates between each treatment group and placebo, the achievement of PASI-75 at Week 12 will be analyzed by 2-sample Fisher's exact test or Chi-square test based on the observed counts. Fisher's exact test will be employed if at least one cell count is smaller than 5. If a participant discontinues from the study prior to Week 12 but has available PASI assessment at the ET visit, the record will be included into the statistical analysis if the ET visit occurred after at least Otherwise, participants without evaluable response due to missing PASI scores at baseline and/or Week 12 will be imputed as non-responder for analysis. The number of participants with imputed response will be provided per treatment group. The absolute count and proportion of participants with moderate-to-severe PsO achieving PASI-75 at Week 12 along with corresponding 2-sided 95% asymptotic and Clopper-Pearson exact CIs will be provided for each treatment group. Table 10.4.3-2 provides a summary of the primary estimand.

Table 10.4.3-2: Primary Estimand

Estimand attribute	Primary		
Treatment	BMS-986322 16 r BMS-986322 32 r BMS-986322 64 r		
Population	Adult male and female participants with moderate-to-severe PsO with or without previous use of biologics		
Endpoint	Percent change from baseline in PASI score ≤ -75% at Week 12 (yes/no)		
Intercurrent event	Event Strategy		Rationale
	Participant discontinuation prior to Week 12		To provide a conservative estimate of the treatment effect assuming early discontinuation due to deterioration of disease

Protocol Amendment No.: 01

Date: 29-Mar-2023 72

Table 10.4.3-2:	Primary Estimand
------------------------	------------------

Estimand attribute	Primary definition	
Population-level summary	Proportion of participants achieving PASI-75 at Week 12	
A 1 1 '	DACLD ' ' A 1C ' I I DO	' ' OD 1'1

Abbreviations: ; PASI, Psoriasis Area and Severity Index; PsO, psoriasis; QD, once daily.

The unstratified odds ratio versus placebo and the difference in the response rates (unstratified risk difference), their associated 2-sided 95% CIs, and p-value from Fisher's exact test or Chi-square test will be provided. There will be no adjustment for multiplicity. All comparisons will be performed in a pre-specified hierarchical procedure starting from the highest dose arm to the lowest dose arm. If a comparison is not significant at level 0.05, all p-values in subsequent comparisons will be considered nominal. As a supportive analysis, the primary efficacy endpoint will be analyzed using the Cochran-Mantel-Haenszel (CMH) test adjusting for the stratification factor prior use of biologics (yes/no) to compare each BMS-986322 treatment group versus placebo. The 2-sided p-values from the CMH test, the adjusted difference in response rates (stratified risk difference) using the weighted average of the treatment differences across the strata with the CMH weights, along with the associated 2-sided 95% CIs using a normal approximation to the weighted average will be provided.

A Cochran-Armitage trend test will be performed to assess a positive trend between treatment groups of BMS-986322 and PASI-75 response rates at Week 12.

As a secondary analysis of the primary endpoint, a logistic regression model analysis will be performed to evaluate the impact of treatment on PASI-75 at Week 12, with treatment group, age, gender, weight, BMI, baseline PASI score, and prior use of biologics (yes/no) as covariates, if applicable. Similar to above, PASI scores observed at ET visits will be included into the analysis. Otherwise, missing observations at Week 12 will not be imputed for analysis. Adjusted odds ratios for each treatment group versus placebo will be provided along with associated 2-sided 95% CIs. Details of the tests and models as well as further analyses of the primary endpoint will be given in the SAP.

Primary safety endpoints will be analyzed by observed incidence and percentage as well as descriptive summary statistics of observed value and change from baseline per treatment group and visit, as applicable. Further details will be given in the SAP.

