10.4.4 Secondary Endpoint(s)

The statistical analysis of dichotomous secondary endpoints, such as achievement of PASI-50, 90, and 100, and achievement of sPGA score of 0 or 1 at Week 12 will in general follow the primary endpoint analysis. To assess dichotomous endpoints over time, a repeated measures logistic regression model analysis will be performed using a generalized estimating equations model.

Continuous secondary endpoints, such as continuous PASI score and BMS-986322 Cmax, AUC(TAU), Tmax, and trough concentrations, will be presented by descriptive summary statistics of value and change from baseline by treatment group and time point, as applicable per parameter.

Protocol Amendment No.: 01

A mixed model for repeated measurements (MMRM) will be employed to assess PASI scores over time. Further details of secondary endpoint analyses including covariates used for model adjustment will be given in the SAP.

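### The normal-approximation 95% CI for the supportive CMH-weighted risk difference covers about 92% at the planning rates (70% v 10%, 30 per arm); a stratified score interval covers about 95%.

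*Combined protocol and SAP*

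**What the plan says.** Protocol section 10.4.3 compares each dose with placebo on PASI-75 at Week 12 by Fisher's exact or the chi-square test. It then adds a stratified analysis by prior biologic use: "As a supportive analysis, the primary efficacy endpoint will be analyzed using the Cochran-Mantel-Haenszel (CMH) test". From that analysis it reports the risk difference averaged over strata with CMH weights, "along with the associated 2-sided 95% CIs using a normal approximation to the weighted average will be provided". No variance formula is named. The section closes the topic with "Details of the tests and models as well as further analyses of the primary endpoint will be given in the SAP", and the document contains no fuller statement.

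Three other places bear on the point:

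- Section 10.2 gives the planning rates ("ie, 70% response rate) compared to placebo assuming the response rate is 10% in the placebo arm") and the size ("approximately 120 participants will be randomized in a 1:1:1:1 ratio").
- Section 10.4.3 has a small-count rule for the test: Fisher's "exact test will be employed if at least one cell count is smaller than 5".
- Section 10.4.4 says that the dichotomous secondary endpoints, which include PASI-50, -90, -100 and sPGA 0/1, "will in general follow the primary endpoint analysis".

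**The concern.** A normal-approximation interval for a difference in proportions tends to cover too little when one arm has few responders. Here 10% of 30 is 3 expected placebo responders, divided between two strata. The chance of fewer than 5 placebo responders is 82% (binomial, 30 at 10%), so the plan's own small-count rule would usually apply to the test, while this interval has no counterpart to it.

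What is at stake is the stated precision of the stratum-adjusted difference from placebo, in a trial whose randomization is stratified on that factor. At the planning rates about three quarters of the misses lie above the true difference, so they overstate the benefit. With low rates in both arms, as may occur for PASI-90 or PASI-100, the direction reverses.

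**Working it through.** **Inputs.** The per-arm number is blank in section 10.2. 120/4 = 30, and the section's own adverse-event figures ("approximately 26%, 79%, and 96% probability of observing at least one occurrence" at 1%, 5% and 10% incidence) confirm it: 1-(1-p)^30 = 26.0%, 78.5% and 95.8%. The stated power of at least 99% is also reproduced: exact enumeration of the two-sided 5% Fisher test at 70% v 10%, 30 per arm, gives 99.88%. Missing Week 12 responses count as non-response, so the denominator stays near 30. The documents give no strata split; 6/24, 9/21, 12/18 and 15/15 per arm are assumptions.

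**Estimator.** In stratum h, with n1 active and n0 placebo participants, x1 and x0 responders and N = n1+n0:

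- w_h = n1·n0/N and W_h = w_h/Σw_h
- d = ΣW_h(p1-p0)

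**Normal-approximation interval.** d ± 1.96·√V, with three usual choices of V:

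- Plain: V = ΣW_h²[p1(1-p1)/n1 + p0(1-p0)/n0]
- n-1: the same with n1-1 and n0-1 as divisors
- Sato: V = (d·ΣP_h + ΣQ_h)/(Σw_h)², where P_h = [n1²x0 - n0²x1 + n1n0(n0-n1)/2]/N² and Q_h = [x1(n0-x0) + x0(n1-x1)]/(2N)

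**Score interval (stratified Miettinen-Nurminen).** All Δ with |d-Δ| ≤ 1.96·√{ΣW_h²·[p̃1(1-p̃1)/n1 + p̃0(1-p̃0)/n0]·N/(N-1)}. Here p̃1 and p̃0 are the maximum likelihood rates in the stratum under p̃1-p̃0 = Δ.

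**Coverage.** Every outcome of the four binomial counts was enumerated and its probability added when the interval held the true difference. No simulation was used. Arms are equal within strata, and rates are common across strata unless stated.

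At 70% v 10%, over the four splits:

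| Interval | Covers | Wholly above truth | Wholly below truth |
|---|---|---|---|
| Plain | 91.9% | 6.1% | 2.0% |
| Sato | 92.1% | 6.0-6.1% | 1.8-1.9% |
| n-1 | 92.4-92.6% | 5.8-6.0% | 1.6% |
| Score | 94.6-94.7% | 2.2-2.3% | 3.0-3.1% |

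Away from the planning point, mean coverage (range over rate pairs):

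| Setting | Plain | Sato | n-1 | Score |
|---|---|---|---|---|
| Active 65-75%, placebo 7-13% (77 pairs) | 92.9% (91.2-94.0) | 93.3-93.4% (91.9-94.4) | 93.6-93.7% (92.1-94.6) | 95.0% (94.3-95.7) |
| Active 30-60%, placebo 7-13% (77 pairs, assumed) | 93.4% (92.5-94.0) | 93.9% (92.9-94.5) | 94.2-94.3% (93.4-94.7) | 95.0% (94.6-95.5) |
| Active 10-35%, placebo 1-3% (55 pairs, assumed) | 92.3-92.4% (88.5-94.0) | 92.8% (88.6-94.5) | 93.1% (88.9-94.8) | 95.9-96.0% (94.8-98.1) |

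Direction of the misses (plain): at 40% v 10% they are nearly balanced (3.6% above, 3.0-3.1% below). In the low-rate setting they average 1.9% above and 5.7-5.8% below.

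Strata with different rates (64% v 4% and 74% v 14%, assumed, either order): plain 91.8-92.3%, n-1 92.3-92.8%, score about 94.5-94.7%.

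**One data set by hand.** 8/12 and 13/18 active v 1/12 and 2/18 placebo. W = 6/15 and 9/15, so d = 0.4·(7/12) + 0.6·(11/18) = 0.600. Plain V = 0.16·0.02488 + 0.36·0.01663 = 0.00997, so √V = 0.0998 and the interval is 0.600 ± 0.196, or 40.4-79.6%. The n-1 form gives 39.7-80.3% and the score interval 37.0-76.3%.

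**The case against.** The strongest reply is that 30 per arm at exactly 70% v 10% is a trough. Coverage moves in a sawtooth with sample size and rates, and the plan says approximately 120. This is right. At 70% v 10% with a 2:1 split and 27 to 33 per arm, coverage runs from 91.9% to 93.7% (plain), 92.2% to 94.4% (Sato) and 92.5% to 94.6% (n-1). The typical shortfall is about 1.5 to 2 points; 3 points belongs to the planning point. The shortfall itself does not go away: no usual form reached 95% at any point checked.

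A second reply is that a normal approximation need not under-cover. Putting (x+0.5)/(n+1) into the variance with n-1 divisors gives about 95.8% at the planning point and a mean of about 95.1% nearby. A pooled variance over-covers, at about 98.6%. Both figures are correct, but the plan selects neither form. The same sentence therefore allows anything from about 92% to 98.6%.

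Third, the carry-over to secondary endpoints is only general, their detail is left to the SAP, and the low rates used here are assumed. That stands as a limit on the secondary-endpoint figures, not on those for the primary endpoint. The Fisher rule governs a test, and Clopper-Pearson intervals are already planned for each arm's rate; neither protects the interval for the adjusted difference.

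Last, no decision is shown to turn on this interval. At the planning rates the chance that its lower limit reaches zero is about 0.03%.

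**Conclusion.** The concern holds. Under each of the three usual variance forms, the interval specified in section 10.4.3 covers less than its label: 91.9-92.6% at the planning rates with 30 per arm, and 92.9-93.7% on average for rates nearby. The score interval covers 94.6-94.7% and 95.0% respectively. The result rests on 30 per arm, which the documents support, and on an assumed strata split, which hardly affects it. The figures for lower-responding doses and for low-rate secondary endpoints rest on assumed response rates. The importance is minor to modest: the precision reported for a supportive estimate is overstated, while the p-values, the dose hierarchy and the conclusion at a 60-point difference are unaffected.

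**What to change.** In the SAP, replace the normal approximation with a stratified Miettinen-Nurminen (score) 95% CI for the risk difference, using the same CMH weights and the N/(N-1) factor in each stratum. Use the same wording for PASI-50, PASI-90, PASI-100 and sPGA 0/1 at Week 12 where they follow the primary analysis. Naming a variance formula alone would not be enough if the formula were one of the three usual forms.

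The cost is SAP wording before database lock, recorded as a change from protocol section 10.4.3. No new data are needed. The interval takes an iterative calculation and is not symmetric about the estimate. In the worked example it moves toward zero. With low rates it moves the other way: for 2/12 and 4/18 v 0/12 and 0/18, from 5.7-34.3% (plain) to 7.2-37.6%. It is slightly conservative when both rates are low, with mean coverage of about 96% and a maximum of 98.1%.
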